## 7.6.2 Secondary Analyses

### 7.6.2.1 Intracellular Concentration Decay

The apparent elimination rate constant ( $k_e$ ), for intracellular phosphates (TFV-DP and FTC-TP) will be determined by estimating the negative slope of the decline in the natural log of concentration between Day 35 and Day 49. Half-life will be estimated as the natural log of 2 divided by the elimination rate constant ( $k_e$ ). These estimates will be performed for each research participant and summarized using descriptive statistics for each arm and the study as a whole. Biological matrices included in the analysis are the same as shown in Table 7-3.

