### 1.2.3 Dosing Duration Rationale

Dose-proportionality can be assessed at any point of observation following initiation of dosing. Intra-individual variability, however, can best be assessed at two sampling times not anticipated to vary based on PK principles. Essentially, by definition, this condition is achieved when steady-state has been reached. This study requires direct observation of dosing to rule out adherence as a cause for variation in drug concentrations. Therefore, we plan to begin sampling for intra-individual variability assessments as early as possible after dosing, balancing logistical difficulties (up to daily dosing for study staff and research participants) and PK limitations. Intracellular TFV-DP concentrations are estimated to achieve between 93% and 97% of steady-state Cmin (trough) concentrations after 4 half-lives and 5 half-lives, respectively, have elapsed after initiation of Truvada® dosing. Based on an estimated 150-hour TFV-DP intracellular half-life (FTC-TP will achieve steady-state earlier, given its far shorter 36-hour half-life), the 4 and 5 half-life points coincide with 28 and 35 days of dosing. Laboratory assay variation for all of the assays planned for this study are more than twice as large as the very small 4% difference in concentrations that we expect to measure between Day 28 and Day 35. Accordingly, we plan to dose for 35 days, and to use samples from Day 28 and Day 35 for our intra-individual variability estimates. One could argue for longer periods of dosing to further reduce differences between doses in the asymptomatic approach to a true steady-state, but we believe that our proposed plan provides a reasonable balance between logistical complexity (daily dosing under direct observation) and reasonable experimental variation.

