### **2.2 Secondary Objectives**

The secondary objectives of this study are to:

- Describe the relationship between pre-dose ( $C_\tau$ ) and decaying concentrations of TFV, FTC, and their phosphorylated derivatives (TFV-DP and FTC-TP) in blood serum, peripheral blood mononuclear cells (PBMCs), CD4+ blood cells, total tissue cells, CD4+ tissue cells, tissue homogenate, semen, and luminal fluid at steady-state (Day 35 [pre-dose] and Day 49 [decaying, greater than one half-life for TFV-DP]).
- Describe differences in intracellular TFV-DP and FTC-TP steady-state  $C_\tau$  between men and women.
- Characterize the safety profiles of four different TDF/FTC PrEP regimens.

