### **2.3.2 Study Sampling**

Sampling will occur over 7 weeks: at enrollment (pre-dose), pre-dose #2 (Day 1 for treatment arm 4, Day 3 for treatment arms 2 and 3, and Day 7 for treatment arm 1) and Days 7, 14, 21, 28, 35 and 49 to support each of the several objectives as follows:

1. Sample blood serum and blood cells (total cells and CD4+ cells) weekly for 5 weeks (Enrollment and Days 7, 14, 21, 28, and 35) to assess rate of accumulation and dose-proportionality in concentrations of extracellular TFV and FTC and intracellular TFV-DP and FTC-TP.
2. Sample blood serum and blood cells at steady-state (Day 28 and Day 35) to assess intra-individual variability.
3. When participants consent to participate in HPTN 066, they will be offered the opportunity to participate in the intensive sampling cohort (to provide mucosal samples). The slots in the intensive sampling cohort will be balanced by gender, so that there will be two men and two women who will undergo mucosal sampling in each of the four arms of the study. Potential research participants who do not choose to participate in or are ineligible for the intensive sampling cohort will be offered participation in the non-intensive cohort. The study team will sample rectosigmoid, seminal and vaginal fluid, cells, and tissue (in addition to blood) at Days 35 and 49 to compare extracellular concentrations of TFV and FTC and intracellular concentrations of TFV-DP and FTC-TP, and to estimate the elimination rate of drug from these compartments.

The sampling described must occur on the days prescribed given the need to synchronize post-dose time (7 days) across the four regimens. The blood sampling time should precede the established dosing time by no more than one hour. If the participant cannot have tissue sampled as prescribed, sampling should take place within the visit window, described in the SSP. In all cases, there must be accurate recording of sample collection times.

Biopsies will not be performed during menstruation. As such, the timing of the first dose will need to take into consideration menstrual patterns and will be adjusted accordingly.

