### 5.3 Non-Intensive Sampling Visits

Table 5-3. Non-Intensive Sampling Visits (Days 1‡, 3‡, 7, 14, 21, 28, 35, and 49)	
Component	Procedure/Analysis
Administrative	
 
• Review/update locator information
 
• Schedule next study visit
 

Clinical	
 
• Collect interval medical/menstrual history
 
• Review/update concomitant medications
 
• Record/update adverse events
 
• Coagulation tests (Day 28 only, see SSP, intensive sampling cohort only)
 
• Perform directed physical exam
 
• Reinforce counseling 
 
◦ Contraception
 
◦ HIV/STI risk reduction and male condom
 
◦ Protocol adherence, product use/adherence
 
 
 
• Provide male condoms
 

Blood	
 
• Pre-dose #2: single blood draw for accumulation index (Day 1 for Treatment Arm 4, Day 3 for Treatment Arms 2 and 3, Day 7 for Treatment Arm 1)†
 
• Safety testing (Days 14, 28, 35 and 49 only, see SSP)
 
• Hepatitis B testing (Day 49 only, see SSP)
 
• Store plasma (Days 28 and 49 only)
 
• HIV testing (Day 49 only)
 
• Collect blood specimens for PK analysis 
 
◦ Serum
 
◦ PBMCs
 
◦ CD4+ blood cells
 
 
 

Urine	
 
• Collect urine sample (women only, Day 28 and 49 only) 
 
◦ Pregnancy testing
 
 
 

Study Product Supply	
 
• Administer study product (if applicable)
 
• Collect unused emergency dose of participant's prepared study product on Day 28 Visit for all arms. Provide a new emergency dose of participants' prepared study product on Day 28 Visit in Treatment Arms 2, 3, and 4.
 
• Collect unused emergency dose of participants' prepared study product on Day 31 Visit for treatment Arms 2 and 3, and on Day 34 Visit for Treatment Arm 4.
 

\* If indicated (see SSP)

† Sample collection for each cohort should be done no more than 1 hour prior to the second dose for each cohort. These will occur on day 7 (Cohort 1), Day 3 (Cohort 2 and 3), and Day 1 (Cohort 4), as indicated.

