### 7.6.1.2 Intra-Participant Variability

Intra-participant variability will be described by the coefficient of variation of concentrations assessed on Day 28 and Day 35, which are assumed to be at steady-state, using data from all evaluable participants across dosing arms. We will confirm that steady-state was achieved by evaluating drug concentration data from Day 7, 14, and 21. If the dose-proportionality is established as described earlier, then dose-adjusted concentrations will be used for a more robust assessment. These variability estimates will be calculated for all analytes in blood and blood cells. As supportive evidence, the accumulation data from Day 7, 14, and 21 will also be used to estimate the elimination rate constant. Tissue and luminal assessments cannot be calculated due to the absence of multiple steady-state samples.

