### Pharmacology

The HPTN NL will perform all drug testing for this protocol. Drugs will be measured in serum, PBMCs, CD4+ blood cells, total tissue cells, CD4+ tissue cells, tissue homogenate, and luminal (vaginal and rectosigmoid) fluid using assays that have an assay validation report (AVR) and SOP approved by the CPQA. Results from these tests will not be returned to study participants.

As described in Section 5, the following types of specimens will be collected for testing at the HPTN NL:

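### Section 7.6.2.1 uses one two-point Day 35 to Day 49 slope for both phosphates, but that gap suits TFV-DP and spans about nine FTC-TP half-lives, so some FTC-TP half-lives may not be estimable

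*Protocol*

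**What the plan says.** Section 7.6.2.1 covers TFV-DP and FTC-TP together. The apparent elimination rate constant "will be determined by estimating the negative slope of the decline in the natural log of concentration between Day 35 and Day 49", and half-life is ln 2 divided by that constant. "These estimates will be performed for each research participant and summarized using descriptive statistics for each arm and the study as a whole". The matrices are those of Table 7-3: PBMCs, CD4+ blood cells, total and CD4+ tissue cells, and homogenate.

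The only reason given for Day 49 is in the secondary objective (Section 2.2): "Day 49 [decaying, greater than one half-life for TFV-DP". FTC-TP is not mentioned there. Section 2.3.2 schedules no sample between Days 35 and 49, and gives as one purpose of the mucosal sampling on those days "and to estimate the elimination rate of drug from these compartments". Section 1.2.3 puts the TFV-DP half-life at 150 h and notes that FTC-TP reaches steady state sooner "given its far shorter 36-hour half-life".

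Two other passages bear on the rate constant. Section 7.6.1.2 says that, as supportive evidence, "the accumulation data from Day 7, 14, and 21 will also be used to estimate the elimination rate constant". Table 5-3 adds a pre-dose #2 sample (Day 1 in Arm 4, Day 3 in Arms 2 and 3, Day 7 in Arm 1), described as a "single blood draw for accumulation index". Neither Section 7.6.1.2 nor Section 7.6.2.1 names that sample.

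**The concern.** A two-point slope exists only if both points can be measured. The gap between them was justified for the analyte with the long half-life and then applied unchanged to one whose half-life is about a quarter as long. For FTC-TP the second point may lie below what the assay can quantify.

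If so, the promised half-life per participant, per arm and overall would be missing for some participants. The loss would not be random, because participants with slow decline or high starting levels stay measurable. A summary of the surviving slopes would then run long, and longer in the arms with lower Day 35 levels. In a study whose main question is dose-proportionality, that pattern could be misread as dose-dependent elimination. Elimination rate is also one stated reason for the Day 35 and Day 49 mucosal sampling, which has four participants per arm (two for vaginal tissue).

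**Working it through.** **Inputs.** Half-lives of 150 h (TFV-DP) and 36 h (FTC-TP): Table 1-1 and Section 1.2.3. Sampling gap: 14 days = 336 h. Dosing days: Arm 1 on Days 0, 7, …, 28 (inferred from five weekly doses); Arms 2 and 3 also on Days 3, 10, …, 31; Arm 4 on Days 0 to 34. A last dose before Day 35 follows from 35 days of dosing (Section 1.2.3) and from the collection of the unused emergency dose on Day 31 (Arms 2 and 3) and Day 34 (Arm 4) in Table 5-3.

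**The plan's own figures first.** Accumulation index = 1/(1 − 2^(−tau/half-life)). TFV-DP daily 9.53 and weekly 1.85; FTC-TP daily 2.70 and weekly 1.04. Table 1-1 gives 9.5, 1.9, 2.7 and 1.0, so the half-lives are used consistently.

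**Fraction left at Day 49** = 2^(−336/half-life).
- TFV-DP: 336/150 = 2.24 half-lives; 2^(−2.24) = 0.212, or 21%.
- FTC-TP: 336/36 = 9.33 half-lives; 2^(−9.33) = 0.00155, or 0.155% (1/645).
- FTC-TP with other half-lives: 30 h leaves 0.04%, 48 h leaves 0.78%, 72 h leaves 3.9%.

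At 36 h, a measurable Day 49 value therefore needs a Day 35 value of at least about 645 times the assay limit.

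**Expected FTC-TP level by arm** (superposition, one-tablet units). With 2^(−24/36) = 0.630 and 2^(−168/36) = 0.0394:
- Arm 4, Day 35: 0.630/(1 − 0.630) = 1.702.
- Arm 2, Day 35: (0.1575 + 0.0394)/(1 − 0.0394) = 0.205. Arm 3 is double, 0.410.
- Arm 1, Day 35: 0.0394/(1 − 0.0394) = 0.0410.

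After the 645-fold fall, Day 49 is 0.155/0.037/0.019/0.0037% of Arm 4's Day 35 level in Arms 4/3/2/1.

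**Illustration of the consequence.** Assumptions: one assay limit for all arms at 0.1% of Arm 4's Day 35 level; no Day 35 dose; lognormal half-life with median 36 h; concentration CV 35%; the Day 35 level follows each person's half-life; 400,000 draws per arm. None of these FTC-TP variances is in the protocol. Section 1.1.5 gives 50% to 65% for TFV-DP half-life, so 65% is shown beside 30%.

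| Arms 4/3/2/1 | Half-life CV 30% | Half-life CV 65% |
|---|---|---|
| Quantifiable at Day 49 | 57/34/24/9% | 54/42/36/25% |
| Median half-life, quantifiable pairs only (true 36 h) | 42/48/51/59 h | 52/58/62/71 h |

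Substituting the limit at CV 30% gives medians of 38/46/51/74 h. The extent moves with the limit: at CV 30%, the quantifiable shares are 79/59/49/26% for a limit of 0.02% and 29/12/6/1% for 0.5%. Below about 0.004%, the median participant of every arm is quantifiable.

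**Can the accumulation data replace the slope?** FTC-TP on Day 7 is at 1 − 2^(−168/36) = 96% of its Day 35 level, so Days 7, 14 and 21 lie on the plateau and say almost nothing about its rate constant. The pre-dose #2 sample does. The expected ratio of Day 35 to pre-dose #2 is 1.702/0.630 = 2.70 in Arm 4 and 0.205/0.25 = 0.82 in Arms 2 and 3. In Arm 1 it is 0.0410/0.0394 = 1.04, which is uninformative.

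**The case against.** **The extent cannot be read from the documents.** Section 9.2 says only that drug levels will be measured "using assays that have an assay validation report (AVR) and SOP approved by the CPQA". A reader might infer that most FTC-TP slopes will be lost. The protocol does not support that, because with a low enough limit the slopes exist and are usable. This stands.

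**The bias needs a rule that the protocol does not state.** A reader might infer that the plan discards or substitutes unquantifiable values. It says neither, and such rules commonly sit in an analysis plan that is not at hand. The overstated half-lives are therefore conditional on handling. What the protocol does fix is the gap and the two-point estimator, and no rule for low values recovers a slope that was not measured.

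**The arm gradient assumes no dose on Day 35.** That is the better-supported reading, but Sections 2.2 and 7.6.1.1 call the Day 35 sample pre-dose, and Section 5.0 ties all sampling to a scheduled dosing time. With a Day 35 dose, 0.25% (Arm 4), 0.91% (Arms 2 and 3) and 3.9% (Arm 1) of the Day 35 pre-dose level would remain. The spread in absolute Day 49 level between arms would shrink from about 42-fold to about 2.6-fold. The shares at the 0.1% limit (CV 30%) would be 65/64/52/49%. The gradient warning would then weaken a good deal, though every fraction would still be far below TFV-DP's 21%.

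**Other routes exist.** The pre-dose #2 sample is drawn for the accumulation index, which Section 1.1.7 links to the rate constant, and Section 1.1.2 plans a multi-compartment model. That is fair, and it is why the fix is cheap. But neither passage sets a method for FTC-TP half-life, and Section 7.6.2.1 does not use them.

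**Conclusion.** The point holds in a limited form. Section 7.6.2.1 fixes for FTC-TP an estimator whose second sample comes 9.33 half-lives after the first, and justifies that sample only for TFV-DP. A Day 35 FTC-TP value below about 645 times the assay limit is expected to yield no slope. This rests on the protocol's 36 h half-life and on no dose being given on Day 35.

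How many participants are affected is unknown without the assay limit. The upward bias arises only if slopes are summarised over quantifiable pairs or with the limit substituted. Its direction held at both half-life CVs tabulated, and its size is illustrative.

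The point is minor. The analysis is secondary and descriptive, with no test or decision attached. A reader might infer that the dose-proportionality conclusion is at risk. It is not, because Section 7.6.1.1 uses Day 35 concentrations. The TFV-DP slope is also sound.

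**What to change.** Amend Section 7.6.2.1 as follows.

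- **TFV-DP:** keep the per-participant Day 35 to Day 49 slope.
- **FTC-TP in PBMCs and CD4+ blood cells:** estimate half-life at arm or pooled level from the pre-dose #2 and later pre-dose samples, with a mono-exponential superposition model. Enter Day 49 as observed if quantifiable and as left-censored if not. This is informative in Arms 2 to 4, but not in Arm 1 alone.
- **FTC-TP in tissue:** report the slope where Day 49 is quantifiable, and otherwise the upper bound 336·ln 2/ln(C35/limit). For example, a Day 35 value of 100 times the limit gives 232.9/4.605 = 50.6 h. Do not summarise over quantifiable pairs only. With two to four participants per arm, a regression model is more than the data can carry.
- **Throughout:** give the number quantifiable per arm and matrix, and do not read arm differences in FTC-TP half-life as dose-dependent elimination.
- State whether a dose is scheduled on Day 35, so that the decay interval is unambiguous.

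**Cost:** some wording and one model on samples already drawn. The blood-cell fit assumes linear mono-exponential kinetics and gives no precise individual half-lives. In simulation with half-life CV 30%, 20% sample noise and the 0.1% limit, the Arm 4 estimate (n = 8) had a 5th to 95th percentile range of 28 to 45 h. That was not repeated at a CV of 50% to 65%, where it would probably be wider. Arm 1 and tissue are only partly repaired.

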### **7.6.2.2 Differences between Men and Women**

Because the genital tracts of men and women differ greatly in terms of anatomy and physiology (e.g. pH differences) as well as drug metabolism, it is feasible that there may be gender-specific differences in the pharmacology of different doses of tenofovir and emtricitabine in different mucosal compartments. Differences in tissue concentrations of these drugs could be relevant in understanding if gender-related differences are detected in intermittent PrEP efficacy trials. Some gender-related differences may be primarily explained by differences in body mass index between men and women, so determining the specific reasons for potential gender-related differences may be challenging with relatively small sample sizes. Men and women will be recruited into the study in equal proportions for comparison. If dose-proportionality is established in the primary objectives, then dose-adjusted Day 35  $C_{\tau}$  concentration differences (each analyte, location, and matrix) between men and women will be tested pooling all research participants using ANOVA. If dose-proportionality is not established in the primary aim, intracellular PK parameters will be summarized by standard descriptive statistics (such as means, medians, and ranges) for each gender within each dose arm. Non-parametric methods may be used to compare  $C_{\tau}$  between men and women. The lack of statistical power of these comparisons due to small sample size is acknowledged.

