**Figure 1-1. Simulation of tenofovir diphosphate (TFV-DP) concentration in PBMCs (y-axis) versus time (x-axis) anticipated with the four different regimens planned for this study: TDF 300 mg daily (blue, QD 300), TDF 600 mg twice weekly (Monday & Thursday, red, BIW 600), TDF 300 mg twice weekly (Monday & Thursday, green, BIW 300), TDF 300 mg weekly (Monday, purple, QW 300); note all regimens are administered as Truvada® (TDF/FTC). Note the minor increase in  $C_{\text{tau}}$  and  $C_{\text{max}}$  between Day 28 and Day 35 where intra-individual variability will be estimated. Simulation parameters are based on data from previous studies (Hawkins et al., 2005; Pruvost et al., 2005; Pruvost et al., 2009). Simulations assume dose-proportionality and do not include intra-individual variation.**

**Figure 1-2. Simulation of tenofovir concentration in blood serum (y-axis) versus time (x-axis) anticipated with the four different regimens planned for this proposal.** The regimens are described in Figure 1-1. Note the near complete overlap in concentration profiles between all regimens on days when the dose is taken. This is due to a very low accumulation index (see text below).

To use the computer modeling methods described above, *two key facts must be determined with regard to the interaction of drug, participant, and regimen: intra-individual variability and dose-proportionality*. Knowledge of these variables is essential for planning future studies that use estimated PK parameters based on individual drug concentrations to evaluate adherence.

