## 5.4 Intensive Sampling Visits

Table 5-4. Intensive Sampling Visit (Days 35 and 49)	
Component	Procedure/Analysis
Administrative	
 
• Review/update locator information
 
• Schedule next study visit
 

Clinical	
 
• Collect interval medical/menstrual history
 
• Review/update concomitant medications
 
• Record/update adverse events
 
• Perform directed physical exam
 
• Perform pelvic exam
 
• Reinforce counseling 
 
○ Contraceptive
 
○ HIV/STI risk reduction and male condom
 
○ Protocol adherence
 
 
 
• Male condoms
 

Blood	
 
• HIV diagnostic testing (Day 49 only, see SSP)
 
• Hepatitis B testing (Day 49 only, see SSP)
 
• Safety testing (see SSP)
 
• Store plasma (Day 49 only)
 
• Collect blood specimens for PK testing 
 
○ Serum
 
○ PBMCs
 
○ CD4+ blood cells
 
 
 

Urine	
 
• Collect urine sample (women only) 
 
○ Pregnancy testing
 
 
 

Vaginal sampling†	
 
• Biopsy, cervical cytobrush, and luminal fluid (see SSP)
 

Rectosigmoid Specimens†	
 
• Flexible sigmoidoscopy with biopsies (up to 30) and collection of luminal fluid (see SSP)
 

Semen†	
 
• Collect semen sample (Men only, see SSP)
 

\*If indicated (see SSP)

†Sixteen of the total 32 participants will participate in the intensive sampling which includes all procedures listed above. The intensive sampling cohort will be divided evenly between men and women from each dosing cohort. For the remaining subjects, that is, the non-intensive cohort, there will be no rectosigmoid, vaginal, or semen sampling on Day 35 and 49.

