**Table 7-1. Power for dose proportionality assessment,  $\alpha = 0.05$**

Sample size (per arm)	CV	Simple linear model and hypothesis testing approach	Power model and CI approach
N=6	25%	93.3%	98.4%
	35%	93.6%	74.9%
	45%	93.2%	33.3%
N=8	25%	95.0%	99.7%
	35%	95.1%	81.1%
	45%	93.8%	41.8%
N=10	25%	95.5%	99.8%
	35%	95.0%	85.0%
	45%	94.4%	43.5%
N=12	25%	96.1%	99.7%
	35%	93.9%	85.2%
	45%	94.6%	43.6%

Simulation results suggested that either 6 or 12 participants per arm would yield sufficient power for a range of coefficient of variation parameters (25% - 45%) when dose proportionality is assessed using hypothesis testing approach based on simple linear regression model. However, the empirical power associated with the power model and the CI approach is more heavily depend on the value of CV in the relevant range. With  $CV \leq 35\%$ , a reasonable degree of variation given the argument above, we would have  $\geq 81\%$  power to claim dose proportionality with 8 participants per arm. For this reason, in addition to cost and operational considerations, 8 subjects per arm was selected as the minimum size to provide adequate power for the dose-proportionality assessment, our primary objective.

For the secondary objective assessing difference in intracellular TFV-DP and FTC-TP steady state Day 35  $C_\tau$  (pre-dose concentration) between men and women, we assume the mean TFV-DP steady state concentration  $C_\tau$  is 100 fmol/ $10^6$  cells, and the coefficient of variation between people is 35%. Based on the results from Van Belle and Martin (Van Belle and Martin, 1993), we would have only 35% power to detect a 1.5 fold difference (i.e., 100 to 150) between men and women within each dosing arm if an arm has 4 men and 4 women (i.e., a total of 32 participants distributed evenly into four arms, 50% men and 50% women). If dose-proportionality holds, then we would be able to make the comparison between men and women across dosing arms. We then would have 89% power to detect a 1.5 fold difference with a total sample size of 32 (16 men and 16 women) selected for this study. Table 7-2 provides power for a range of CV, sample size and minimal detectable difference. The power would reduce with smaller sample size, smaller minimal detectable difference, and larger CV.

**Table 7-2. Power to detect the minimal detectable difference (in fold) for various sample sizes and coefficients of variance (CV)**

CV	N per group	Minimal detectable X-fold difference		

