## **7.4 Study Arm Assignment**

At the time of consent, subjects will designate whether they will participate in the non-intensive or intensive sampling cohort. Assignment prioritization will go to the intensive sampling cohort. Within each of these 2 cohorts and each gender stratum, enrolled participants will be assigned at random to one of the four study arms in a 1:1:1:1 ratio. The permuted block randomization scheme will not be stratified by site and will be generated and maintained by the HPTN SDMC. For each randomized participant who is not fully evaluable (see section 7.3) an additional participant of the same gender will be enrolled into the same arm and the same cohort (intensive or non-intensive sampling). Details of the randomization system will be in the SSP Manual.

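### The pooled men-versus-women test of Day 35 Cτ depends on declaring dose-proportionality; with arm as a factor it needs no such condition, and for FTC-TP the protocol's own half-life and schedule rule the test out

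*Protocol*

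**What the plan says.** Describing gender differences in intracellular TFV-DP and FTC-TP Cτ is a named secondary objective (Protocol Section 2.2). Section 7.6.2.2 gives two routes. If dose-proportionality is established, dose-adjusted Day 35 Cτ "between men and women will be tested pooling all research participants using ANOVA". If not: "If dose-proportionality is not established in the primary aim, intracellular PK parameters will be summarized by standard descriptive statistics", for each gender within each arm. Non-parametric methods are then optional, with no stratification named, and low power is acknowledged.

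Section 7.3 repeats the condition: "If dose-proportionality holds, then we would be able to make the comparison between men and women across dosing arms". It attaches 89% power (16 vs 16) to that route and gives 35% within an arm (4 vs 4), for a 1.5-fold difference at CV 35%.

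Section 7.6.1.1 judges proportionality on Day 35 pre-dose concentration: the 90% CI of the power-model slope must lie within 0.64 to 1.36. Section 7.4 describes the allocation: "Within each of these 2 cohorts and each gender stratum, enrolled participants will be assigned at random to one of the four study arms".

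**The concern.** Whether concentration rises in proportion to dose and whether men and women differ at a given dose are separate questions. The plan makes an answer to the second depend on a favourable answer to the first.

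Pooling across arms needs the arm differences removed. Dividing by dose does this only under proportionality; a four-level arm factor does it under any dose-concentration shape. Because gender is balanced within arm, gender and arm are orthogonal and the factor costs almost nothing. The one assumption it needs, a common gender ratio across arms, is already made by the planned pooled ANOVA.

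The condition may also fail because of trough timing. The pre-dose sample on Day 35 falls at very different times after the last dose in the four arms, which steepens the slope even when kinetics are linear. The effect is greatest for the analyte with the short half-life. At stake is one of the two intracellular analytes in the objective, and part of the power for the other.

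**Working it through.** **Protocol's own power.** At constant CV 35% and means of 100 and 150, the common SD is 35·√((1+1.5²)/2) = 44.6. With a two-sided 0.05 test (assumed; the level is not stated for Table 7-2) and the normal approximation:
- 16 vs 16: z = 50/(44.6·√(2/16)) = 3.17, power Φ(3.17 − 1.96) = 0.887 (stated 89%).
- 4 vs 4: z = 50/(44.6·√(2/4)) = 1.585, power Φ(1.585 − 1.96) = 0.354 (stated 35%).

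Both reproduce.

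**Expected Day 35 troughs under linear kinetics.** Inputs:
- Half-lives of 150 h (TFV-DP) and 36 h (FTC-TP), from Table 1-1. Section 1.2.3 confirms the second: "FTC-TP will achieve steady-state earlier, given its far shorter 36-hour half-life".
- Twice-weekly doses on Monday and Thursday (Figure 1-1 legend), that is Days 0 and 3 of each week.
- Table 5-3 collects unused emergency doses "on Day 31 Visit for treatment Arms 2 and 3, and on Day 34 Visit for Treatment Arm 4", which marks the last dosing days. Day 28 for Arm 1 follows from weekly dosing.
- The last dose is therefore 168, 96, 96 and 24 h before the Day 35 sample in Arms 1 to 4.

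Trough = Σ dose × 2^(−time since dose / half-life). For FTC-TP, 2^(−168/36) = 0.0394, 2^(−96/36) = 0.1575 and 2^(−24/36) = 0.6300, and accumulation is essentially complete, so:
- Arm 1: 0.0394/0.9606 = 0.0410
- Arm 2: (0.0394 + 0.1575)/0.9606 = 0.2049
- Arm 3: twice Arm 2 = 0.4099
- Arm 4: 0.6300/0.3700 = 1.7024

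Summing the TFV-DP doses from Day 0 gives 0.835, 1.999, 3.997 and 8.350.

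The slope is the least-squares slope of log ratio on log(1, 2, 4, 7), where Σ(x − x̄)² = 2.138.

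| Analyte | Trough ratios, Arms 1–4 | Slope | Limits |
|---|---|---|---|
| TFV-DP | 1 : 2.4 : 4.8 : 10 | 2.486/2.138 = 1.16 | 0.64–1.36 |
| FTC-TP | 1 : 5 : 10 : 41.5 | 3.872/2.138 = 1.81 | 0.64–1.36 |

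A slope of 1.36 would need a half-life of about 73 h, twice the stated FTC-TP value.

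**Power of the two plans.** 40,000 simulated trials, 4 men and 4 women per arm, true gender ratio 1.5, two-sided 0.05. Conditional plan: the 90% CI of the slope must lie within the limits, then ANOVA of Cτ/dose on gender (30 df); an unmet condition counts as no pooled test. Alternative: log Cτ on arm factor plus gender (27 df). The log-normal SD is σ = √ln(1 + CV²), or 0.340 at CV 35%.

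| True Cτ pattern | Errors | CV | Conditional plan | Arm + gender |
|---|---|---|---|---|
| Proportional | log-normal | 35% | 87% | 90% |
| Proportional | log-normal | 45% | 60% | 73% |
| Proportional | normal (Section 7.3) | 35% | 74% | 75% |
| Proportional | normal | 45% | 41% | 53% |
| TFV-DP ratios | log-normal | 25% | 83% | 99% |
| TFV-DP ratios | log-normal | 35% | 55% | 90% |
| TFV-DP ratios | log-normal | 45% | 33% | 73% |
| TFV-DP ratios | normal | 35% | 44% | 75% |
| FTC-TP ratios | log-normal | 35% | 0% | 90% |
| FTC-TP ratios | normal | 35% | 0% | 74% |

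With no gender difference, the arm-plus-gender model rejects in about 5% of trials at either set of ratios.

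At the TFV-DP ratios and CV 35% (log-normal), the condition is met in 64% of trials with a 1.5-fold gender effect and in 74% without one. The power model has no gender term, so a real gender difference widens its CI and makes the test less likely to be reached.

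**Precision (log-normal, CV 35%).** Arm plus gender: SE = 0.340·√(2/16) = 0.120, t(27 df) = 2.05, 95% CI ×/÷ exp(0.247) = 1.28. One arm, 4 vs 4: SE = 0.340·√(2/4) = 0.240, t(6 df) = 2.45, giving ×/÷1.80 with σ inserted, or ×/÷1.76 at the average estimated SD; power is 30% by t-test on logs.

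**Unequal gender ratios.** With true ratios of 1.25, 1.4, 1.6 and 1.8 in Arms 1 to 4, the model estimates their geometric mean, (1.25 × 1.4 × 1.6 × 1.8)^(1/4) = 1.50, with 89% power.

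**The case against.** The strongest reply is that the fallback does not forbid an all-arm comparison. Section 7.6.2.2 permits non-parametric methods without naming a stratum, and a rank test stratified by arm would have about 86% power with log-normal data at CV 35%. The 0% for FTC-TP therefore means that the planned pooled test is not reached, not that no comparison is possible. That is correct. But the comparison is optional and unspecified, and Section 7.3 presents the alternative to pooling as 4 vs 4 within an arm.

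Second, the objective is to describe, and low power is admitted. This limits the severity. The admission attributes the low power to sample size, however, and does not disclose that the schedule itself is expected to rule out the FTC-TP test. Description also suffers, as the interval widths show.

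Third, most of the loss comes from judging proportionality on troughs at unequal post-dose times, which is an issue for the primary analysis. With true proportionality at CV 35% the two plans are nearly equal. That stands. The gender comparison nevertheless need not inherit the problem, and at CV 45% the conditional plan loses power even under exact proportionality.

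Fourth, Section 2.3.2 speaks of synchronising post-dose time at 7 days. Read as a Day 28 last dose in every arm, this gives slopes of 0.85 (TFV-DP) and 0.55 (FTC-TP). The TFV-DP figures depend on the reading; FTC-TP still falls outside the limits. Figure 1-1 and Table 5-3 support the schedule used here.

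Fifth, a common gender ratio is least assured when kinetics are not proportional. That is fair, and is why the within-arm summaries should stay.

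**Conclusion.** The concern holds. The condition is unnecessary, because a balanced arm factor pools all participants without it. At CV 35% with log-normal data, the chance of reaching the pooled test and detecting a 1.5-fold difference falls from 90% to 55% for TFV-DP and to 0% for FTC-TP. If Cτ is truly proportional the loss is small (87% vs 90%).

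These figures rest on one-compartment superposition with a single half-life per analyte, the dosing days above, an unmet condition counted as no pooled test, and proportionality judged analyte by analyte. The last is suggested by Section 7.6.2.2 but not spelled out. With the protocol's normal errors the alternative has 75% power, not 90%, at CV 35%, but the ordering at the TFV-DP and FTC-TP ratios is unchanged. Since the objective is secondary and descriptive, this should be changed but does not endanger the primary analysis.

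**What to change.** Replace the conditional rule in Section 7.6.2.2, and the matching sentence in Section 7.3, with wording such as:

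> For every analyte and matrix measured in both sexes, the gender ratio of Day 35 Cτ with its 95% CI will be estimated from log Cτ = arm (four-level factor) + gender, in all evaluable participants contributing that matrix, whether or not dose-proportionality is declared. Sampling cohort is added for blood matrices only. The model assumes one gender ratio across arms; summaries by gender within arm are kept to examine this.

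State also that mucosal comparisons come from the intensive cohort alone ("Sixteen of the total 32 participants will participate in the intensive sampling"): 8 vs 8, 16 − 5 = 11 residual df, and about 58% power at the same CV and ratio. If a non-parametric test is kept, stratify it by arm.

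Dropping the condition but keeping linear dose-adjustment without an arm term would not be enough: at the FTC-TP ratios and CV 35% it has about 17% power on the log scale.

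The cost is wording only. Residual degrees of freedom fall from 30 to 27, or to 26 with sampling cohort in the blood models; with log-normal data at CV 35%, power stays at 90% either way.
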